7.4 Concurrent Therapies

7.4.1 Required and/or Permitted

The following medications and procedures are permitted during the study:

- Anti-emetic medications (with the exception of dexamethasone and/or other steroids) are permitted at the treating physician's discretion.
- Subjects are permitted the use of topical, ocular/auricular, intra-articular, intranasal, inhalational steroids, also systemic steroid dose of oral prednisone ≤ 10 mg daily or equivalent, as well as any adrenal replacement steroid dose all in the absence of active autoimmune disease.
- Colony stimulating growth factors (i.e. erythropoietin, darbepoetin, pegfilgrastim) are permitted at the treating physician's discretion. Their use should follow American Society of Clinical Oncology (ASCO) guidelines and/or label indications/institutional practice.
- Patients should be transfused with red cells and platelets as clinically indicated and according to institutional guidelines. However, transfusions may not be used to satisfy inclusion criteria for study entry.
- Treatment with full-dose anticoagulation therapy (i.e. warfarin, enoxaparin, rivaroxaban, etc.) are permitted at the treating physician's discretion.
- Supportive measures consistent with optimal patient care may be given throughout the study.

7.4.2 Prohibited and/or Restricted Treatments

- Immunosuppressive agents are prohibited during the study, unless they are utilized to treat an adverse event or as outlined in Section 7.4.1. NSAIDs for treatment of osteoarthritis and allopurinol to prevent gout flares is allowed.
- Concurrent administration of any anti-cancer therapies (investigational or approved) are also prohibited with the exception of subjects in the follow-up period of the study.
- Any medicinal herbal preparation unless prescribed by the treating physician. All concomitant medications including prescribed medicinal herbal preparations must be documented.
- G-CSF (granulocyte-colony stimulating factor) will be permitted. However, the use of these agents is allowed as per their respective label indications/institutional guidelines to treat neutropenia that occurs on study. G-CSF must not be used for the treatment of cancer or for any primary prophylaxis while on study.

7.4.3 Other Restrictions and Precautions

- Any non-oncology live viral vaccine therapies used for the prevention of infectious diseases within 4 weeks prior to study drug is prohibited. The use of the killed/inactivated vaccines, e.g. seasonal influenza vaccine will be permitted on study without restriction.
- Alcohol consumption while on study is strongly discouraged due to the potential to confound interpretation of hepatotoxic events.

8. Study Duration and Discontinuation of Therapy

8.1 Study Duration

Patients will receive protocol therapy unless:

1. Disease progression per RECIST Version 1.1 criteria or clinical progression.
2. Toxicities considered unacceptable by either the patient or the investigator, despite optimal supportive care and dose delays.
3. Any requirement to discontinue based on dose delay guidelines in Section 7.1, Section 7.2, infusion reaction guidelines in Section 7.3 and Appendix III.
4. Development of an inter-current illness that prevents further administration of study treatment.
5. Extraordinary Medical Circumstances: If at any time the constraints of this protocol are detrimental to the patient's health, protocol treatment should be discontinued.
6. Patient withdraws consent or is unable to comply with study procedures.

8.2 Duration of Follow-Up

Patients will be followed for adverse events for 100 days after their last dose of neoadjuvant treatment. Adverse events may be reviewed at the next visit \geq 100 days after last dose of neoadjuvant therapy or phone follow-up may be done to review adverse events. However, if a patient experiences an adverse event $>$ 100 days after their last dose of study medication that is felt to be, in the opinion of the investigator, possibly, probably or definitely related to study therapy, the adverse event should be reported.

Patients will be followed clinically and radiographically per standard of care (3 -6 months) at the discretion of the treating physician for at least 2 years post-cystectomy or when study-wide follow-up ends. Date of diagnosis for progression, first subsequent therapy and survival shall be reported. Phone follow-up may also be done for patients unable or unwilling to return for follow-up evaluations.

If a patient is removed from treatment for reason(s) other than progression, follow with regular tumor assessments per standard of care until progression or start of new treatment.

For patients who are registered but do not receive any protocol therapy, baseline and follow-up information per Section 11 will be collected.

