5.3 Expected Duration of Treatment and Patient Participation

Following registration, patients in each group will receive a total of 4 weeks of neoadjuvant therapy followed by RC with bilateral (standard or extended) PLND as soon as possible but within 6 weeks of the completion of neoadjuvant therapy.

Off treatment visit will occur approximately 30 days following cystectomy (if cystectomy is not performed, Off Treatment visit should be performed at next scheduled appointment or treating physician discretion, as clinically indicated) and patients will be followed for 100 days after neoadjuvant treatment for AEs. Adverse events may be reviewed at the next visit ≥ 100 days after last dose of neoadjuvant therapy or phone follow-up may be done to review adverse events.

Patients will be followed clinically and radiographically for at least 2 years post-cystectomy or when study-wide follow-up ends per standard of care. Date of diagnosis for progression, first subsequent therapy and survival shall be reported. Phone follow-up may also be done for patients unable or unwilling to return for follow-up evaluations.

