8.3 Criteria for Removal from Study Treatment

A genuine effort will be made to determine the reason(s) why a patient fails to return for the necessary visits or is discontinued from the trial, should this occur. It will be documented whether or not each patient completed the clinical study. If for any patient study treatment or observations were discontinued, the reason will be recorded on the appropriate eCRF. Reasons that a patient may discontinue treatment in a clinical study are considered to constitute one of the following:

1. Completion of all study therapy and follow-up.
2. Recurrence of disease or documented progression of disease.
3. Intercurrent illness that prevents further administration of treatment per investigator discretion.
4. Unacceptable adverse events.
5. Investigator and/or patient discontinue study therapy.
6. Pregnancy.

7. Develops a second malignancy (except low risk cervical cancer or cancer in-situ) that requires treatment, which would interfere with this study.
8. The patient may choose to withdraw from the study at any time for any reason.
9. General or specific changes in the patient's condition that render the patient unacceptable for further treatment in the judgment of the investigator.
10. Severe non-compliance to protocol as judged by the investigator.
11. Lost to follow-up.
12. Death.
13. Closure of study by PrECOG.

Any patient who receives at least one dose of nivolumab or lirilumab will be included in the safety analysis. Patients who discontinue study treatment early should be followed for response assessments, if possible. Follow-up will continue per Section 11, as applicable.

9. Adverse Event Reporting

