- 14 Radical cystectomy with bilateral (standard or extended) pelvic lymph node dissection to be performed as soon as possible but within 6 weeks after the last neoadjuvant infusion.

- 15 Obtain CTs (or MRI as noted above) after second dose of nivolumab +/- lirilumab and before surgery.

- 16 Thirty (30) days +/- 7 days after cystectomy. If patient is removed from treatment for reason(s) other than progression, follow with regular tumor assessments per standard of care until progression or start of new treatment. Once a patient has initiated a new therapy, no further imaging assessments for this study are required.

NOTE: If cystectomy is not performed, Off Treatment visit should be performed at next scheduled appointment or treating physician discretion, as clinically indicated.

- 17 Patients will be followed for adverse events for 100 days after their last dose of neoadjuvant therapy. Adverse events may be reviewed at the next visit \geq 100 days after last dose of neoadjuvant therapy or phone follow-up may be done to review adverse events. However, an adverse event occurring at any time after discontinuation of study therapy that is felt to be at least possibly related to study therapy should be recorded.

- 18 Patients will be followed clinically and radiographically per standard of care (every 3-6 months) at the discretion of the treating physician for at least 2 years post-cystectomy or when study-wide follow-up ends. Date of diagnosis for progression, first subsequent therapy and survival shall be reported. Phone follow-up may also be done for patients unable or unwilling to return for follow-up evaluations.

12. Drug Formulation and Procurement

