13.2.3 Additional Secondary Objectives

1. The average percentage (%) change in the CD8+ TIL density from TURBT to RC in each of the two cohorts. Each individual patient's percent change will be defined as $[(\text{Cystectomy TIL Density}) - (\text{TURBT TIL Density})] / (\text{TURBT TIL Density})$.
2. Proportion of patients in each cohort who do not get a radical cystectomy specifically and directly related to treatment related AEs within 6 weeks of the last dose of neoadjuvant treatment.
3. Proportion of patients with pathologic complete (pT0N0) and partial (<pT2N0) response in the two cohorts.
4. Proportion of patients who are alive and free of disease in each cohort at 2 years from registration.

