### **7.7. Efficacy Analysis**

All Efficacy analyses are performed for efficacy population except Recurrent-Free Survival and Overall Survival analyses. The RFS and OS analyses are performed for safety population.

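### The only 2-year follow-up minimum starts at cystectomy, yet RFS and OS cover all treated patients; non-operated patients who start other therapy may leave RFS well before 2 years

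*Protocol*

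**What the plan says.** **The minimum.** Protocol 5.3 reads: "Patients will be followed clinically and radiographically for at least 2 years post-cystectomy or when study-wide follow-up ends per standard of care". Protocol 8.2 ("at the discretion of the treating physician for at least 2 years post-cystectomy or when study-wide follow-up ends") and Section 11 footnote 18 ("for at least 2 years post-cystectomy or when study-wide follow-up ends") carry the same anchor, as do SAP 4.1 and SAP Appendix I footnote 18. No 2-year minimum is stated from any other starting point.

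**The analysis set and landmark.** SAP 7.7 says "The RFS and OS analyses are performed for safety population". SAP 7.5.1 defines that population as all patients with at least one dose, so surgery is not required. Protocol 13.2.3 lists as a secondary endpoint: "Proportion of patients who are alive and free of disease in each cohort at 2 years from registration". SAP 7.7.5 adds a 2-year OS estimate for each cohort.

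**Patients without surgery.** The plan foresees them: Protocol 5.3 and Section 11 footnote 16 place their Off Treatment visit at the next appointment or at the physician's discretion. Four rules then bear on them:
- If removed from treatment for a reason other than progression, sites are to "follow with regular tumor assessments per standard of care until progression or start of new treatment" (Protocol 8.2, repeated in Section 11 footnote 16).
- Footnote 16 continues: "Once a patient has initiated a new therapy, no further imaging assessments for this study are required".
- After early discontinuation, "Follow-up will continue per Section 11, as applicable" (Protocol 8.3).
- Protocol 8.2 requires the dates of progression, first subsequent therapy and survival to be reported, allows telephone follow-up, and sets adverse event follow-up at 100 days after the last dose.

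**Censoring.** RFS is censored at the last RECIST assessment (SAP 7.7.4), and OS at the date the patient was last known to be alive (SAP 7.7.5).

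**The concern.** A patient who is treated but never operated on is in the RFS and OS populations, yet the 2-year clock has no start date for that patient. Protocol 8.3 refers early discontinuers to Section 11, where the 2-year duration is again counted from surgery.

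Patients who miss surgery because of toxicity, refusal or lost fitness plausibly do worse than those who have it. If they leave RFS observation when they start other therapy, Kaplan-Meier carries them forward at the event rate of the patients still observed, and 2-year RFS comes out too high. The cohorts are compared by log-rank test, and missed surgery due to related adverse events is itself a secondary endpoint that may differ between them, so the distortion need not be equal.

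SAP 7.7.4 also displays the proportion recurrence-free at two years from registration. SAP 7.3 leaves missing data unimputed, and nothing says how unknown 2-year status is handled. Outcome data that were never collected cannot be recovered at analysis.

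**Working it through.** The documents give no event rate, power or no-surgery rate for RFS or OS, so there is no stated figure to reproduce. The check uses dates from the protocol windows and then a bias calculation under stated assumptions.

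**1. Dates, in days from first dose, against a 730-day landmark.**
- Operated patients: second dose on day 28 (week 4) and surgery within 6 weeks, so by day 28 + 42 = 70. Two years after surgery falls between 28 + 730 = day 758 and 70 + 730 = day 800. The cystectomy anchor does operated patients on schedule no harm.
- Non-operated patients: the fixed adverse event period ends on day 28 + 100 = 128 after two doses (128/730 = 17.5% of the landmark) or day 100 after one dose (13.7%). Tumor assessments have an end condition, not a duration. The last RECIST scan could be the one after the second dose and before planned surgery (Section 11 footnote 15), between week 4 and about week 10.

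**2. Bias in 2-year RFS.** Assumptions: exponential event times; 2-year event-free proportion S₁(24) = 0.70 with surgery and S₀(24) = 0.30 without; a fraction f without surgery, all censored at month c; operated patients followed past 24 months; progression before censoring counted as an event in both groups.

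Truth = (1 − f)·S₁(24) + f·S₀(24).

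Kaplan-Meier limit = [(1 − f)·S₁(c) + f·S₀(c)] × S₁(24)/S₁(c).

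Bias = f × [S₁(24)·S₀(c)/S₁(c) − S₀(24)].

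At c = 4: S₁ = 0.70^(1/6) = 0.942, S₀ = 0.30^(1/6) = 0.818, ratio 0.868. Bias = f × (0.70 × 0.868 − 0.30) = 0.308f.

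At c = 12: ratio = (0.30/0.70)^(1/2) = 0.655. Bias = f × (0.70 × 0.655 − 0.30) = 0.158f.

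| f | True 2-year RFS | Kaplan-Meier, c = 4 | Bias, c = 4 | Bias, c = 12 |
|---|---|---|---|---|
| 10% | 66.0% | 69.1% | +3.1 | +1.6 |
| 15% | 64.0% | 68.6% | +4.6 | +2.4 |
| 20% | 62.0% | 68.2% | +6.2 | +3.2 |

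(Biases in percentage points.) For scale, the binomial standard error at 62% is √(0.62 × 0.38/24) = 9.9 points in Cohort 2 and √(0.62 × 0.38/12) = 14.0 points in Cohort 1. The largest bias shown is therefore about 0.6 and 0.4 of a standard error.

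**3. Bounds for single cohorts.** Assume about 35% events among operated patients and every non-operated patient censored before the first event.
- Cohort 2, 4 of 24 without surgery, 7 events in 20: Kaplan-Meier 13/20 = 0.650. The true proportion is 13/24 = 0.542 if all four have events and 17/24 = 0.708 if none does.
- Cohort 2, 2 of 24, 8 events in 22: 14/22 = 0.636, range 14/24 = 0.583 to 16/24 = 0.667.
- Cohort 1, 2 of 12, 4 events in 10: 6/10 = 0.600, range 6/12 = 0.500 to 8/12 = 0.667.

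**4. Event definition.** Protocol 10.7 and SAP 5.6 count recurrence only after radical cystectomy, or death. Progression in a patient never operated on is therefore not clearly an RFS event, so following such a patient to progression may still leave only a censored time.

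**The case against.** A reader might infer that non-operated patients have no follow-up at all and are necessarily censored within months, inflating both RFS and OS. The documents do not support that.
- The paragraphs around the 2-year rule in Protocol 8.2 require tumor assessments after removal for reasons other than progression, which covers toxicity, refusal and lost fitness where these lead to removal from treatment.
- Survival reporting is not restricted by surgery. Survival status is a follow-up row in the Section 11 schedule, and Protocol 8.2 collects follow-up even for registered patients who receive no therapy.
- No section ends follow-up for non-operated patients.
- OS runs to the date last known alive, telephone contact counts, and nothing stops survival reporting at new therapy. Early OS censoring does not follow from the text.

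All of that stands. It does not supply a duration. Survival reporting has no stated end point for these patients. The alternative limb, the end of study-wide follow-up, might be read as governing patients with no cystectomy date, but it sets no minimum. The tumor-assessment rule stops at new treatment and does not reach patients removed for progression. A patient who completes both doses and then has no surgery is not clearly removed from treatment.

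It is also fair that the size rests entirely on assumed inputs, that later censoring roughly halves it, and that this is a small non-randomised Phase Ib trial with a safety primary endpoint. RFS is secondary and has no stated power, and OS is not among the listed objectives. Finally, telephone calls alone would not move a RECIST censoring date, so a remedy confined to follow-up wording would miss the RFS mechanism.

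**Conclusion.** The concern holds in a limited form. No fixed follow-up to the 2-year landmark is written for treated patients without cystectomy, although they are in the RFS and OS analyses. For RFS, permission to stop imaging at new therapy, combined with censoring at the last RECIST assessment, means the plan followed as written can censor non-operated patients informatively. The bias would be upward if they do worse than operated patients: about 3 to 6 points with censoring at 4 months, and about 1.6 to 3.2 with censoring at 12 months. These figures assume 10% to 20% without surgery, a 70% versus 30% split, and all non-operated patients censored at the stated time. If only some start other therapy and leave imaging early, the bias shrinks in proportion.

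The bias is smaller than the sampling error of either cohort, but it is systematic and avoidable. OS is less affected, and operated patients on schedule are not affected. The change should be made; the safety primary endpoint does not depend on it.

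**What to change.** - **Follow-up (Protocol 5.3, 8.2 and Section 11 footnote 18; SAP 4.1 and Appendix I footnote 18).** State that all treated patients, with or without cystectomy and including after new therapy, have disease status (from standard-of-care imaging or chart review) and survival collected to at least 2 years from the endpoint's time origin.
- **Time origin.** Reconcile it. Protocol 10.7 and SAP 5.6 start RFS at first treatment; Protocol 2.2, 13.2.3 and 13.2.3.1 and SAP 7.4.2.5 start it at registration; SAP 7.7.4 uses both.
- **Censoring (SAP 7.7.4).** Censor RFS at the last documented disease-status assessment instead of the last RECIST assessment, so that status collected after new therapy counts.
- **Event definition (Protocol 10.7; SAP 5.6 and 7.7.4).** State how progression in a patient without cystectomy counts, since recurrence is now defined only after cystectomy.

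The cost is a wording change in both documents and a few extra chart reviews or telephone contacts for a small number of patients. Telephone follow-up is already permitted, and no new procedure is needed.

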8.3 Criteria for Removal from Study Treatment

A genuine effort will be made to determine the reason(s) why a patient fails to return for the necessary visits or is discontinued from the trial, should this occur. It will be documented whether or not each patient completed the clinical study. If for any patient study treatment or observations were discontinued, the reason will be recorded on the appropriate eCRF. Reasons that a patient may discontinue treatment in a clinical study are considered to constitute one of the following:

1. Completion of all study therapy and follow-up.
2. Recurrence of disease or documented progression of disease.
3. Intercurrent illness that prevents further administration of treatment per investigator discretion.
4. Unacceptable adverse events.
5. Investigator and/or patient discontinue study therapy.
6. Pregnancy.

7. Develops a second malignancy (except low risk cervical cancer or cancer in-situ) that requires treatment, which would interfere with this study.
8. The patient may choose to withdraw from the study at any time for any reason.
9. General or specific changes in the patient's condition that render the patient unacceptable for further treatment in the judgment of the investigator.
10. Severe non-compliance to protocol as judged by the investigator.
11. Lost to follow-up.
12. Death.
13. Closure of study by PrECOG.

Any patient who receives at least one dose of nivolumab or lirilumab will be included in the safety analysis. Patients who discontinue study treatment early should be followed for response assessments, if possible. Follow-up will continue per Section 11, as applicable.

9. Adverse Event Reporting

9.1 Collection of Safety Information

Adverse Event (AE) is defined as any new untoward medical occurrence or worsening of a pre-existing medical condition in a patient administered a medicinal product in a clinical investigation and which does not necessarily have a causal relationship with this treatment. An AE can therefore be any unfavorable and unintended sign (e.g., including an abnormal laboratory finding), symptom, or disease temporally associated with the use of a product (investigational or marketed), whether or not considered related to the product (investigational or marketed).

After informed consent, but prior to initiation of study treatment (nivolumab and lirilumab), only AEs/SAEs caused by a protocol-mandated intervention will be collected (e.g., SAEs related to invasive procedures such as biopsies). After the initiation of study treatment, all identified AEs and SAEs must be recorded and described on the appropriate page of the electronic Case Report Form (eCRF). If known, the diagnosis of the underlying illness or disorder should be recorded, rather than individual symptoms. The following information should be documented for all AEs: date of onset and resolution, severity of the event; the investigator's opinion of the relationship to investigational product (see definitions below); treatment required for the AE; cause of the event (if known); and information regarding resolution/outcome.

Only clinically significant laboratory abnormalities that require active management will be recorded as AEs or SAEs on the eCRF (e.g., abnormalities that require study drug dose delay, discontinuation of study treatment, more-frequent follow-up assessments, further diagnostic investigation, etc.).

If the clinically significant laboratory abnormality is a sign of a disease or syndrome (e.g., alkaline phosphatase and bilirubin 5x the ULN associated with cholecystitis), only the diagnosis (e.g., cholecystitis) needs to be recorded on the Adverse Event eCRF.

If the clinically significant laboratory abnormality is not a sign of a disease or syndrome, the abnormality itself should be recorded as an AE or SAE on the eCRF. If the laboratory abnormality can be characterized by a precise clinical term, the clinical term should be recorded as the AE or SAE. For example, an elevated serum potassium level of 7.0 mEq/L should be recorded as "hyperkalemia".

Observations of the same clinically significant laboratory abnormality from visit to visit should not be repeatedly recorded as AEs or SAEs on the eCRF unless their severity, seriousness, or etiology changes.

Severity

The categories and definitions of severity used for clinical trials AEs are defined in the NCI's Common Terminology Criteria (CTCAE) V5.0 (<http://www.ctep.cancer.gov>).

Attribution

The following categories and definitions of causal relationship or attribution to study drug should be used to assess Adverse Events:

- **Definite:** There is a reasonable causal relationship between the study drug and the event. The event response to withdrawal of study drug (dechallenge) and recurs with rechallenge, if clinically feasible.
- **Probable:** There is a reasonable causal relationship between the study drug and the event. The event responds to dechallenge. Rechallenge is not required.
- **Possible:** There is a reasonable causal relationship between the study drug and the event. Dechallenge information is lacking or unclear.

- Unlikely: There is doubtful causal relationship between the study drug and the event.
- Unrelated: There is clearly not a causal relationship between the study drug and the event or there is a causal relationship between another drug, concurrent disease, or circumstances and the event.

Categories 'definite', 'probable' and 'possible' are considered study drug related. Categories 'unlikely' and 'unrelated' are considered not study drug-related.

The development of a new cancer should be regarded as an AE. New cancers are those that are not the primary reason for administration of study treatment and have been identified after inclusion of the patient into the clinical study.

AEs related to nivolumab and lirilumab should be followed for 100 days after last dose of study therapy until \leq grade 1 or stabilization, and reported as SAEs if they become serious. Any AE's (serious or not) that occur more than 100 days after the last dose of study therapy but that are deemed to be at least possibly related to study therapy shall be reported.

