2.1 Primary Objective

To assess safety of treatment according to Common Terminology Criteria for Adverse Events version 5.0 (CTCAE v5.0) manifested as the rate of Grade 3 or higher treatment related adverse events in patients treated with nivolumab (Cohort 1) or combination of nivolumab/lirilumab (Cohort 2).

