6.1.3 Name of Other Modality or Procedures

All patients enrolled in this trial will undergo a RC with bilateral (standard or extended) PLND as soon as possible but within 6 weeks of the last dose of neoadjuvant therapy as outlined above.

7. Dose Delays

All toxicities should be graded according to the National Cancer Institute (NCI) Common Terminology Criteria for Adverse Events Version 5.0 (CTCAE V5.0). A copy of the CTCAE V5.0 can be downloaded from the CTEP website (<http://www.ctep.cancer.gov>).

A +/-3 day window is allowed for scheduled therapy, required tests and/or visits except as otherwise noted. Delays due to holidays, weekends, bad weather or other unforeseen circumstances will be permitted.

Dose delays are not required for adverse events not deemed to be related to study treatment (i.e. events due to underlying disease) or for laboratory abnormalities not deemed to be clinically significant. Treat accordingly per institutional standards.

Any patient who cannot receive study therapy within 6 weeks from the previous dose in either cohort, will be permanently discontinued, except as noted below.

NO dose modifications will be allowed.

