7.2.2 Grade 3 Toxicities

Subjects will be required to permanently discontinue all study drugs for the following AEs:

- Any Grade 3 non-skin, drug-related AE lasting >7 days or recurs, with the following clarifications:
 - Grade 3 drug-related uveitis, pneumonitis, myocarditis, bronchospasm, hypersensitivity reaction, or infusion reaction of any duration requires discontinuation.
 - Grade 3 drug-related endocrinopathies, adequately controlled with only physiologic hormone replacement, do not require discontinuation. Adrenal insufficiency requires discontinuation regardless of control with hormone replacement.
 - Grade 3 drug-related laboratory abnormalities do not require treatment discontinuation except:
 - Grade ≥ 3 drug-related AST, ALT, or total bilirubin
 - Concurrent AST or ALT $>3x$ ULN and total bilirubin $>2x$ ULN

For any other Grade 3 treatment related non-hematologic toxicities, if the Grade 3 toxicity does not resolve to \leq Grade 1 within 21 days, all study therapy will be **permanently discontinued**.

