#### **7.6.7. Clinical Laboratory Data**

Numeric clinical laboratory data will be summarized at each visit (clinical data collection point) using descriptive statistics. Non-numeric laboratory tests will be summarized separately using frequency counts on unique responses. Individual change from baseline in lab values will be calculated and summarized descriptively. The Lab shift table will be displayed at each visit for each laboratory test.

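### The AE recording filter has no override by grade, so some drug-related Grade 3 laboratory values, mainly non-hepatic chemistry, can be missing from the primary Grade 3+ rate

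*Protocol*

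**What the plan says.** Protocol 2.1 sets the primary objective as safety by CTCAE v5.0, "manifested as the rate of Grade 3 or higher treatment related adverse events", in each cohort. SAP 7.6.6.1 analyses this as a proportion during neoadjuvant treatment with a 90% exact binomial interval.

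Protocol 9.1 first defines adverse events broadly: "An AE can therefore be any unfavorable and unintended sign (e.g., including an abnormal laboratory finding), symptom, or disease temporally associated". It then narrows what is captured: "Only clinically significant laboratory abnormalities that require active management will be recorded as AEs or SAEs on the eCRF". The examples of such management are "abnormalities that require study drug dose delay, discontinuation of study treatment, more-frequent follow-up assessments, further diagnostic investigation, etc". SAP 6.1 repeats the rule. Neither document adds that a result of a given CTCAE grade is always recorded.

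Two passages on dosing bear on which laboratory results call for action. The opening of Protocol Section 7 says dose delays are not required for events unrelated to treatment "or for laboratory abnormalities not deemed to be clinically significant", with no grade limit. Protocol 7.2.2 says "Grade 3 drug-related laboratory abnormalities do not require treatment discontinuation except" for Grade 3 or higher AST, ALT or total bilirubin and for a concurrent transaminase and bilirubin elevation.

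SAP 7.6.7 summarises laboratory values and changes from baseline by visit, and adds: "The Lab shift table will be displayed at each visit for each laboratory test". It mentions neither CTCAE grading nor any link to the primary endpoint.

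**The concern.** The endpoint is defined by grade, but entry to the data that feed it depends on a site judgement of significance and need for management. Two patients with the same drug-related Grade 3 value could be counted differently. A value that never becomes an AE record receives no attribution. The SAP 7.3 rule that treats missing attribution as related cannot rescue it, because that rule works only on AEs already recorded.

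An omission can only lower the reported rate. The trial is open-label, the cohorts are sequential and small, and about eight sites take part, so uneven capture could affect the one result the study is designed to estimate.

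**Working it through.** **Step 1: the plan's own figures.** For x events in n patients, the exact 90% limits are: lower = 5th percentile of Beta(x, n−x+1); upper = 95th percentile of Beta(x+1, n−x). The width is greatest at x = n/2.

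- n=12, x=6: width 0.509 (plan: 0.51).
- n=24, x=12: width 0.361 (plan: 0.36).

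Both figures reproduce, and this point does not dispute them.

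**Step 2: which Grade 3+ laboratory results should reach the AE form while doses remain.**

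| Result | Passage | Action stated | Should be recorded? |
|---|---|---|---|
| Grade 3 hematologic | Protocol 7.1.2 | Therapy withheld or stopped | Yes |
| Grade 4 hematologic | 7.1.3 | Permanent discontinuation | Yes |
| Grade 3+ AST, ALT, bilirubin | 7.2.2 | Discontinuation | Yes |
| Qualifying liver injury | 9.4 | SAE report | Yes |
| Grade 4 non-hematologic | 7.2.3 | Discontinuation, two listed exceptions | Mostly yes |
| Grade 3 non-hepatic chemistry | 7.2.2 | Discontinuation not required | Only if judged significant and needing management |

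The Section 11 panel includes sodium, potassium, glucose, calcium, creatinine and uric acid, so the last row is not empty. The exemption at the start of Section 7 has no grade limit, and the text does not say how it fits with the mandatory rules in 7.1 and 7.2. Those passages need to be reconciled.

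**Step 3: after dose 2.** Section 11 schedules CBC and chemistry at Infusion 2, Surgery and Off Treatment once treatment has begun. The last two of these three draws fall after the final dose. Dose delay and discontinuation, two of the four listed examples of management, can no longer apply; closer follow-up and further investigation still can. Whether these draws count depends on when neoadjuvant treatment ends for the primary endpoint, which neither document states.

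**Step 4: size per patient.** One patient whose only related Grade 3+ event is an unrecorded laboratory value changes the rate by 1/12 = 8.3 points or 1/24 = 4.2 points.

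**Step 5: illustration.** Protocol 1.6 cites a Grade 3-4 treatment-related rate of 24/159 = 15% for the combination. That corresponds to 12 × 24/159 = 1.8 and 24 × 24/159 = 3.6 patients, so take 2 and 4 as recorded counts. The number omitted is an assumption.

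| Assumed omitted | Cohort 1 with them counted (90% CI) | Cohort 2 with them counted (90% CI) |
|---|---|---|
| 0 | 2/12 = 16.7% (3.0-43.8) | 4/24 = 16.7% (5.9-34.2) |
| 1 | 3/12 = 25.0% (7.2-52.7) | 5/24 = 20.8% (8.6-38.9) |
| 2 | 4/12 = 33.3% (12.3-60.9) | 6/24 = 25.0% (11.5-43.5) |

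**The case against.** The strongest reply is that there is no contradiction. The objective promises a rate of adverse events, Section 9.1 defines which laboratory findings are recorded as adverse events, and CTCAE grades are applied to those. This is a coherent collection rule. The management test is also broad: a repeat test or a diagnostic work-up prompted by the value is enough, and both remain possible throughout the 100-day AE follow-up. To be lost, a value must be thought drug-related yet need neither. Laboratory toxicity is not hidden either, since SAP 7.6.7 tabulates every test at every visit. The separate TFL template may define shift categories by CTCAE grade, and it is not available here. The primary rate is descriptive, with no threshold or test, and the illustrated intervals overlap heavily.

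Most of this stands, and it limits the point. It does not close the gap. No passage guarantees that a Grade 3+ value is recorded, and even a graded shift table would carry no attribution and would not enter the primary numerator as SAP 7.6.6.1 is written.

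A reader might infer that Grade 3-4 laboratory results in general escape the endpoint. The Section 7 rules and Protocol 9.4 do not support that while dosing continues. A reader might also infer that the primary rate is known to be understated. The documents give no count of omitted patients, so only the possibility is established.

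**Conclusion.** The point holds in limited form. The recording filter lets a drug-related Grade 3+ laboratory value be absent from the primary rate, and nothing in the stated analysis recovers it. The exposure is chiefly Grade 3 non-hepatic chemistry, plus values after dose 2 if the primary window includes them.

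The size is 8.3 points per affected patient in Cohort 1 and 4.2 points in Cohort 2. This assumes the planned 12 and 24 treated patients, and that each affected patient has no other recorded related Grade 3+ event. The number of such patients is unknown and may be zero. The interval method and stated widths are correct. The matter should be addressed before database lock, but it does not invalidate the endpoint.

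**What to change.** Amend the analysis and leave the recording rule as it is.

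1. In SAP 7.6.7, derive CTCAE v5.0 grades from the laboratory data already collected, in the same way for both cohorts. SAP 6.3 describes laboratory collection by cycles up to cycle 9; align it with the two-infusion schedule in SAP Appendix I so that the derivation uses the actual visits.
2. In SAP 7.6.6.1, state when the primary window ends.
3. Before lock, check every Grade 3+ value that is worse than baseline and inside that window against the AE file. Where no AE exists, query the site for attribution.
4. Report per cohort, beside the primary rate, a rate with a 90% exact interval that also counts related Grade 3+ laboratory values.

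Section 9.1 should not be changed for Cohort 2 alone. Protocol 6.1 and 12.1.5 show that Cohort 1 has been treated and Cohort 2 has begun, so a new rule now would give the cohorts different capture. The cost is some site queries, one extra table and a possibly less favourable rate. If nothing was missed, the check documents that the primary rate is complete in this respect.
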